An interim analysis is planned after all participants receiving SC administration in Part 1 complete their Week 24 visit. At that time point, the data available for participants receiving IV administration will also be analyzed and included.

Brief Summary:

The purpose of this study is to assess the safety, tolerability, and PK of a single 20 mg/kg or **CCI** [REDACTED] or a single 60 mg/kg IV dose of GSK3810109, in healthy adult participants.

- Study duration: Up to 24 weeks excluding screening
- Treatment duration:
 - For Part 1, single SC infusion on Day 1 that is expected to take 3 to 15 minutes to administer.
 - For Part 2, single IV infusion on Day 1, that is expected to take approximately 60 minutes to administer; the entire infusion should not exceed 2 hours.
 - **CCI** [REDACTED]

Number of Participants:

A sufficient number of participants will be enrolled to ensure that approximately 8 participants complete each part of the study for a total of approximately 24 participants in the study.

Participants who withdraw prior to study completion may be replaced.

Note: Enrolled means a participant's agreement to participate in a clinical study following completion of the informed consent process and all screening activities. Potential participants who are screened for the purpose of determining eligibility for the study, but do not participate in the study, are not considered enrolled. A participant will be considered enrolled if the informed consent is not withdrawn prior to participating in any study activity after screening.

Intervention Groups and Duration:

The study duration will be 24 weeks (excluding screening) and the study product will be administered on Day 1 of each part.

Data Monitoring/ Other Committee: No Data and Safety Monitoring Board will be empaneled for this study

[figure not shown]
An SRT for GSK3810109 reviews emerging and cumulative data for GSK3810109 on a monthly basis. For Part 1, safety review decisions and the status of the enrollment process will be shared with an SRT at regular intervals and discussed during the monthly SRT meetings.

For Part 2, a core SRT for Study 217901 will review data for both sentinel and non-sentinel participants of the study. [CC1]

[REDACTED] The core SRT is composed of safety lead, medical monitors, and project biostatistician.

[figure not shown]

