| PIN and NRS ⁶ | | | | X | | | X | | | X | | | | | | | | | | |
| 12-lead ECG ⁷ | X | | X | | X | | X | X | X | | | | X | | | | | X | | |
| Clinical laboratory ⁵ | X | X | | | | | X | | | X | X | | X | | | X | | X | X | |
| Urinalysis ⁵ | X | X | | | | | | | | X | | | | | | | | | | |
| Pregnancy test:(serum) (POCBP only) ⁸ | X | X | | | | | X | | | X | X | | X | X | X | X | X | X | X | |
| FSH ⁹ | X | | | | | | | | | | | | | | | | | | | |
| HIV and hepatitis B and C ⁵ | X | | | | | | | | | | | | | | | | | | | |
| Test for SARS-CoV-2 ¹⁰ | X | X | | | | | | | | | | | | | | | | | | |

| Visit Number | | | 01 | 01A | 01B | 01C | 02 | 03 | 04 | 05 | 06 | 07 | 08 | 09 | 10 | 11 | 12 | 13 | ED = early discontinuation/withdrawal | |
|---------------------------------------------------------------------------|--------------------------|----------|---------------------|-------------|-----|-----|------|------|------|-----|-----|-----------|-----|-----|------|------|------|------|---------------------------------------|--|
| Time From Start of SC Infusion | | | Pre | SOI | 4hr | 8hr | 24hr | 48hr | 72hr | Wk1 | Wk2 | Wk3 | Wk4 | Wk8 | Wk12 | Wk16 | Wk20 | Wk24 | | |
| Day of Study ¹ | | D-1 | D1 | D1 | D1 | D1 | D2 | D3 | D4 | D7 | D14 | D21 | D28 | D56 | D84 | D112 | D140 | D168 | | |
| Clinical Activity | Screen Days -21 to -2 | Check-in | Intervention Period | | | | | | | | | Follow-up | | | | | | | | |
| Timed PK sample ¹¹ | | | X | X | X | | X | X | X | X | X | X | X | X | X | X | X | X | | |
| CCI [REDACTED] sample collection | | | X | | | | | | | | | | X | X | X | X | X | X | | |
| Recording of injection site reactions in 14 days diary card ¹² | | | | ←————→————— | | | | | | | | | | | | | | | | |
| Recording of AEs/SAEs ¹³ | | | | ←————→————— | | | | | | | | | | | | | | | | |
| Concomitant medication review | | | X | X | X | | X | X | X | X | X | X | X | X | X | X | X | X | | |

AE = adverse event; BMI = body mass index; COVID-19 = coronavirus disease; FSH = follicle-stimulating hormone; HIV = human immunodeficiency virus-1; ISR = injection site reaction; NRS = Numeric Rating Scale; PIN = Perception of Injection PK = pharmacokinetic(s); POCBP = participant of childbearing potential; SAE = serious adverse event; SARS-CoV-2 = severe acute respiratory syndrome-related coronavirus-2; SC = subcutaneous; SOI = start of infusion

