The overall compartmental half-life ($t_{1/2\beta}$) of GSK3810109 is currently estimated to be 44 ± 6 days for IV administration and offers the potential for an ultra-long-acting target profile. Ultra-long-acting ART, defined as 3 to 6 months or longer, can help to improve treatment adherence, which is the most important determinant for sustained viral suppression, a decrease in the frequency of clinic visits, and reduction in the social stigma associated with daily therapy. Based on PK estimates from the VRC 609 study and the antiviral effect of GSK3810109 at 280 mg in HIV viremic individuals in Study 207959 (BANNER), it is estimated that a 40 mg/kg IV dosing may be able to provide coverage for 4 months but is unlikely to provide sufficient therapeutic breadth for a 6-month

dosing interval. Pharmacokinetic modelling suggests GSK3810109 given at 60 mg/kg may be adequate for every 6 months administration.

[figure not shown]
A 60 mg/kg dose of GSK3810109 will exceed the 40 mg/kg no-observed-adverse-effect level (NOAEL) set by ViiV Healthcare. The NOAEL set by the VRC is at 400 mg/kg IV and has been endorsed by the FDA. Based on the same VRC generated data, ViiV set the NOAEL at 40 mg/kg due to the morbidity of 1 male rat at 400 mg/kg, for which it was not possible to exclude a relationship to exposure. A review of observed GSK3810109 Cmax and area under the plasma concentration-time curve (AUC) exposure in humans at 40 mg/kg IV found levels to be appreciably higher than rodent exposures at the 40 mg/kg NOAEL and raises questions of the relevancy of the rodent model PK as a basis for lowering the NOAEL from 400 mg/kg to 40 mg/kg. In addition, simulated PopPK modeling shows that 60 mg/kg IV in humans is predicted to have a lower Cmax than the VRC 400 mg/kg rat NOAEL Cmax. This model was used to simulate GSK3810109 serum concentrations of 60 mg/kg IV dosing in a population of adults with a range of bodyweights representative of the anticipated volunteer population for Study 217901. Predicted individual serum concentration versus time profiles predict that after a 60 mg/kg dose, serum concentrations of GSK3810109 in all individuals will be below the average Cmax from 40 mg/kg dosing within 3 days (i.e., 72 hours) of study product administration.

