7. DISCONTINUATION OF STUDY INTERVENTION AND PARTICIPANT DISCONTINUATION/WITHDRAWAL

7.1. Discontinuation of Study Intervention

Emerging safety data will be reviewed in-stream as the study progresses and the following criteria will result in a study pause. A full safety review will be conducted, and the findings and recommendations presented to ViiV Safety and Labelling Committee (VSLC) for endorsement:

- Any SAE, regardless of its severity, that is considered be clinically significant and reasonably attributable to dosing with GSK3810109, in the opinion of the investigator and sponsor.
- Acute allergic reaction or CRS (Division of AIDS [DAIDS] criteria Grade 3 to 4) reasonably attributable to dosing with GSK3810109, in the opinion of the investigator and sponsor.
- Any AE of Grade 4 intensity assessed as related to GSK3810109, as reported by the investigator.
- Any participant meeting liver chemistry stopping criteria (see Section [7.2](#))
- Any participant meeting QTcF stopping criteria (see Section [7.3](#))
- If 2 participants in any discrete part of the study (Part 1, Part 2, or Part 3) experience an AE of Grade 3 intensity (excluding ISRs) assessed as related by the investigator.
- If 2 or more injections/infusions administered in any discrete part of the study (Part 1, Part 2, or Part 3) are followed by an ISR of at least Grade 3 in severity.

Note: Grade 3 ISRs that are based on the size of erythema or induration alone will not be considered as a pausing criterion. However, any Grade 3 ISR of erythema or induration due to ulceration, secondary infection, phlebitis, sterile abscess, drainage, or symptoms causing inability to perform usual social and functional activities (as per DAIDS) will be included as a pausing criterion.

Relevant reporting and discussion with the Medical Monitor, relevant study team personnel, and the institutional review board (IRB)/independent ethics committee (IEC) will take place before resumption of dosing. Every effort will be made to take a blood sample at the time of the AE for PK analysis.

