7.2. Liver Chemistry Stopping Criteria

Liver chemistry stopping and increased monitoring criteria have been designed to assure participant safety and evaluate liver event etiology (in alignment with the FDA pre-marketing clinical liver safety guidance [[DHHS, 2009](#)]).

Discontinuation of GSK3810109 is not possible for abnormal liver tests as this is a single-dose study. If a participant meets liver chemistry stopping criteria, the study will pause to conduct an evaluation of the relevant safety data. The findings and recommendations on dosing resumption will be presented to VSLC for endorsement.

Liver Chemistry Stopping Criteria

- ALT $\geq 3 \times$ ULN
- If ALT $\geq 3 \times$ ULN AND bilirubin $\geq 2 \times$ ULN ($>35\%$ direct bilirubin) or international normalized ration >1.5 , report as an SAE.

Refer to Section [10.5](#) for required Liver Safety Actions and Follow up Assessments.

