| 
 • Immediately pause study • Report the event to ViiV/GSK within 24 hours • Complete the liver event eCRF, and complete an SAE data collection tool if the event also meets the criteria for an SAE² • Perform liver event follow-up assessments • Monitor the participant until liver chemistries resolve, stabilize, or return to within baseline (see MONITORING below) 
MONITORING:
 
If ALT $\geq 3 \times$ ULN AND bilirubin $\geq 2 \times$ ULN or INR >1.5:
 
 • Repeat liver chemistries (include ALT, AST, alkaline phosphatase, bilirubin, and INR) and perform liver event follow-up assessments within 24 hours • Monitor participant twice weekly until liver chemistries resolve, stabilize or return to within baseline • A specialist or hepatology consultation is recommended 
If ALT $\geq 3 \times$ ULN AND bilirubin $< 2 \times$ ULN and INR ≤ 1.5:
 
 • Repeat liver chemistries (include ALT, AST, alkaline phosphatase, bilirubin and INR) and perform liver event follow-up assessments within 24 to 72 hours • Monitor participant weekly until liver chemistries resolve, stabilize or return to within baseline | 
 • Viral hepatitis serology³ • Obtain INR and recheck with each liver chemistry assessment until the aminotransferase values show downward trend • Obtain blood sample for PK analysis, obtained within 48 hours of last dose⁴ • Serum creatine phosphokinase and lactate dehydrogenase • Fractionate bilirubin, if total bilirubin $\geq 2 \times$ ULN • Obtain complete blood count with differential to assess eosinophilia • Record the appearance or worsening of clinical symptoms of liver injury, or hypersensitivity, on the AE report form • Record use of concomitant medications on the concomitant medications report form including acetaminophen, herbal remedies, other over-the-counter medications • Record alcohol use on the liver event alcohol intake eCRF 
If ALT $\geq 3 \times$ ULN AND bilirubin $\geq 2 \times$ ULN or INR >1.5:
 
 • Anti-nuclear antibody, anti-smooth muscle antibody, Type 1 anti-liver kidney microsomal antibodies, and quantitative total immunoglobulin G or gamma globulins. • Liver imaging (ultrasound, magnetic resonance, or computerized tomography) and /or liver biopsy to evaluate liver disease; complete liver imaging and/or liver biopsy eCRF. |

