1. Serum bilirubin fractionation should be performed if testing is available. Additionally, if serum bilirubin fractionation testing is unavailable, record presence of detectable urinary bilirubin on dipstick, indicating direct bilirubin elevations and suggesting liver injury.
2. All events of ALT $\geq 3 \times$ ULN and bilirubin $\geq 2 \times$ ULN ($>35\%$ direct bilirubin) or ALT $\geq 3 \times$ ULN and INR >1.5 , which may indicate severe liver injury (possible "Hy's Law"), must be reported as an SAE (excluding studies of hepatic impairment or cirrhosis); the INR threshold value stated will not apply to participants receiving anticoagulants.
3. Includes: hepatitis A immunoglobulin (IgM) antibody, hepatitis B surface antigen, and hepatitis B core antibody; hepatitis C RNA; cytomegalovirus IgM antibody; Epstein-Barr viral capsid antigen IgM antibody (or if unavailable, obtain heterophile antibody or monospot testing) and hepatitis E IgM antibody.
4. Pharmacokinetic sample may not be required for participants known to be receiving placebo or non- ViiV/GSK comparator interventions. Record the date/time of the PK blood sample draw and the date/time of the last dose of study intervention prior to PK blood sample draw in the eCRF. If the date or time of the last dose is unclear, provide the participant's best approximation. If the date/time of the last dose cannot be approximated OR a PK sample cannot be collected in the time period indicated above, do not obtain a PK sample. Instructions for sample handling and shipping are in the Study Reference Manual.

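### Appendix 5 bars the event-triggered PK sample for any liver event more than 48 hours after the single dose, which contradicts Section 7.1

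*Protocol*

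**What the plan says.** Protocol 10.5 (Appendix 5) lists the follow-up assessments for a liver stopping event. One of them reads "Obtain blood sample for PK analysis, obtained within 48 hours of last dose". Footnote 4 adds that if "a PK sample cannot be collected in the time period indicated above, do not obtain a PK sample".

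Section 7.1 lists "Any participant meeting liver chemistry stopping criteria" among the criteria that pause the study. It closes with a sampling instruction that has no time limit: "Every effort will be made to take a blood sample at the time of the AE for PK analysis".

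Section 7.2 notes that "Discontinuation of GSK3810109 is not possible for abnormal liver tests as this is a single-dose study". The last dose is therefore always the Day 1 dose. Follow-up runs to Week 24 (Synopsis: "Study duration: Up to 24 weeks excluding screening"). Section 4.3 gives a half-life that "is currently estimated to be 44 ± 6 days for IV administration".

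Two other provisions bear on the point. Section 8.3 allows additional PK samples if they are warranted and the investigator and sponsor agree. Section 8 allows unscheduled samples for safety reasons.

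**The concern.** A limit counted from the last dose suits repeated dosing, where the last dose is usually recent. Here it closes two days after the only dose and never reopens, while liver chemistry is followed for months. The appendix is the page a site will open when an event occurs. Read literally, it tells the site not to take the sample that Section 7.1 wants.

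ALT/AST elevation is a primary endpoint in every part, and one participant with ALT at or above 3 times the upper limit of normal pauses the study. With about 8 participants per part, each such event carries weight. Part 2 also uses a single dose above the 40 mg/kg maximum given before. The committee deciding whether dosing resumes would want to know exposure at the event.

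**Working it through.** The plan states no figure on this point to reproduce. The check asks how much of follow-up the bar covers, how far scheduled sampling fills the gap, and whether a late sample would be useful.

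**1. The window.** Day 1 to Day 168 is 167 days. The share later than 48 hours is 1 − 2/167 = 98.8%.

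**2. Early events.** The first Part 1 laboratory test after dosing is on Day 2, at 24 hours. For an isolated ALT elevation, 10.5 sets the liver repeat and follow-up assessments, which include the PK sample, within 24 to 72 hours. Counted from a Day 2 finding, that is 24 + 24 = 48 to 24 + 72 = 96 hours after dosing, at or past the limit.

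**3. Scheduled laboratory days and scheduled PK draws.** These are read from the Schedules of Activities (Protocol 1.5 to 1.7), excluding early-discontinuation visits and counting Day 3 as inside the window. The Part 2 arrow is taken as daily from Day 2 to Day 8.

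| Part | Post-dose laboratory days | After Day 3 | Of these, PK on the same day | No PK |
|---|---|---|---|---|
| 1 | 2, 7, 14, 28, 112, 168 | 5 of 6 | 5 of 5 | none |
| 2, non-sentinel | 2 to 8, 14, 28, 84, 140 | 9 of 11 | 6 of 9 | 5, 6, 8 |
| 2, sentinel | as above, plus 10 | 10 of 12 | 6 of 10 | 5, 6, 8, 10 |
| 3 | 2, 3, 4, 7, 14, 28, 84, 140, 168 | 7 of 9 | 7 of 7 | none |

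If the Day 3 visit falls outside 48 hours, the late counts become 5 of 6, 10 of 11, 11 of 12 and 8 of 9. The last column does not change, because PK is drawn on Day 3. At early discontinuation, Part 1 marks laboratory tests but no PK, while Parts 2 and 3 mark PK. No PK is scheduled for unscheduled visits, for the 24-hour or 24-to-72-hour liver repeats, or for weekly or twice-weekly liver monitoring.

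**4. Share of events.** The documents give no onset times. Assume uniform onset, with detection at the next scheduled laboratory test.
- Part 1: 166/167 = 99.4% are detected after 48 hours, all with same-day PK.
- Part 2: 137/139 = 98.6% are detected after 48 hours. Of these, 134/137 = 97.8% (non-sentinel) or 132/137 = 96.4% (sentinel) have same-day PK.
- Part 3: 165/167 = 98.8% are detected after 48 hours, all with same-day PK.

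Under this assumption the event-triggered sample is barred for nearly all events, but a scheduled sample exists on the day of detection for 96% to 100% of those detected late.

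**5. Would a late sample be informative?** A rough one-phase figure, for IV only, is 0.5^((day − 1)/44), with the range for half-lives of 50 to 38 days.
- Day 28: 0.5^(27/44) = 65% (61% to 69%).
- Day 168: 0.5^(167/44) = 7% (5% to 10%).

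These figures describe terminal decline, not the fraction of peak serum concentration. Section 4.3 predicts that after 60 mg/kg all participants fall below the average 40 mg/kg peak within 72 hours. If peak is proportional to dose, that is 40/60, or two-thirds of the average peak, at most. The figures also do not describe the SC profile in Parts 1 and 3. The assay's quantification limit is not given, but the plan itself schedules PK to Day 168, so it treats late concentrations as worth measuring.

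**The case against.** A reader might infer that nearly every liver event would go without an exposure sample. The schedules do not support that. Most late laboratory days carry a PK draw, and that draw serves as a sample at the time of the event. The share of events affected also depends on onset times that the documents do not give.

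A reader might also infer that the protocol forbids any late PK sample. It does not. Sections 8.3 and 8 permit extra samples, and Section 8.5 allows immunogenicity serum, including serum from the final visit of a withdrawn participant, to be assayed for concentration. That could partly cover the Part 1 early-discontinuation gap. Section 7.1 is itself only a best-effort statement.

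The remaining gaps can often be bridged. Days 5 and 6 lie between draws on Days 4 and 7, and Days 8 and 10 between draws on Days 7 and 14. After Day 28 scheduled draws are at most 28 days apart, or 28/44 = 0.64 of a half-life. No primary analysis needs the sample, because ALT/AST incidence is counted without PK (Protocol 9.3.2, SAP 4.2.2).

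All of this limits the consequence, and most of it stands. It does not remove the contradiction. A general permission that needs agreement is weak against a specific instruction not to sample, and Section 8 allows no waivers. Interpolation needs the next scheduled draw, which may come weeks after the pause, and it assumes an undisturbed decline. Footnote 4 also mentions placebo and comparator participants, whom this study does not have. That suggests, but does not prove, generic text that was not adapted.

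**Conclusion.** The contradiction between 10.5 with footnote 4 and Section 7.1 is explicit, and 10.5 also sits badly with Section 8.3. It applies to every liver event later than about Day 3. What is lost is the event-triggered sample, not exposure data in general. The gap is confined to the unscheduled contacts, the Part 2 days and the Part 1 early-discontinuation visit identified above.

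The conflict rests on the text alone. The share of events does not: it assumes uniform onset and detection at scheduled tests. The day counts come from tables extracted from PDF, so the column alignment should be checked against the original. The decay figures are a one-phase approximation for IV dosing, and they support only the statement that a late sample is likely to be informative. The primary endpoint analysis is unaffected. The point is worth correcting because it serves the pause review at very little cost.

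**What to change.** Reconcile 10.5 and footnote 4 with Sections 7.1 and 8.3. In the list of follow-up assessments, remove the limit of 48 hours from the last dose. In footnote 4, remove the clause that bars a sample outside that period. State instead that a PK sample is drawn when the liver event is identified or at the first liver repeat, with the time since dose recorded. Footnote 4 already asks for the dates and times of dose and sample.

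The cost is a wording change in one table entry and one footnote, plus at most about one 2 mL tube per liver event, taken at a draw already required and counted within the 500 mL limit in Section 8. The planned summary tables are unaffected, because SAP 4.1 keeps unscheduled visits out of them and includes those visits in listings.

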10.6. Appendix 6: COVID-19 Pandemic and Clinical Study Continuity

The COVID-19 pandemic may impact the conduct of clinical studies. Significant logistical challenges may arise from quarantines, variable restrictions on site resources and operations, site closures, travel limitations and the inability of an individual participant to attend clinic visits, interruptions to the supply chain for the investigational product, or other considerations if site personnel or study participants become infected with COVID-19. These challenges may lead to difficulties in meeting protocol-specified procedures, including dispensation of the investigational product to the participant or adhering to protocol-mandated visits and laboratory/diagnostic testing.

Based on these challenges, it may be necessary to adopt additional measures and procedures to protect participant safety, and to ensure that there are no gaps in study treatment for participants enrolled in this clinical study.

In order to maintain the scientific integrity of the study and adhere to updated guidance from regulators, procedures have also been put into place to ensure that the actions taken to mitigate against any impact of COVID-19 are well documented in the study database.

This appendix outlines the measures that are approved for implementation within this clinical study, to protect participant safety, welfare, and rights, and to ensure data integrity and the integrity of the clinical study, as a result of COVID-19 only. These measures may be implemented in accordance with any requirements and expectations set out by local IRBs/IECs and National Competent Authorities, as necessary.

This appendix does not apply to participant management issues that are unrelated to a specific, and documented, impact from COVID-19.

